#### **8.2.5.2 Statistical Methods for Immunogenicity Analyses**

There are no formal immunogenicity hypotheses comparing the vaccination groups since it is anticipated that placebo recipients will have anti-HPV titers below the limit of detection of the cLIA and total IgG assay.

#### Estimation of seroconversion percentage

The seroconversion percentages with respect to anti-HPV 6, 11, 16, 18, by Month 7 will be evaluated by computing point estimates and constructing 95% CI. Calculation of the CI is based on the exact binomial method proposed by Clopper and Pearson (1934).

#### Estimation of GMTs

Anti-HPV 6, 11, 16, 18 GMT at Month 7 will be evaluated by computing point estimates and constructing 95% CI. The values will be log transformed before analysis. As such, the CI for the means will be constructed on the natural log scale and will reference the t-distribution. Exponentiating the means and lower and upper limits of these CI will yield estimates for the population GMT and CI about the GMT on the original scale.

#### Persistence of immune responses

Anti-HPV 6, 11, 16, 18 GMTs and seroconversion percentages at Months 7 and 36 will be summarized in the PPI population to assess the persistence of immune responses. Longitudinal plots of the GMTs from Day 1 through Month 36 will also be provided for graphical display.

### **8.2.5.3 Statistical Methods for Safety Analyses**

All subjects who received at least one injection and have follow-up data will be included in the analysis of safety, including protocol violators and subjects discontinuing from the study. The following approach will be used for the analysis of safety parameters across all injections.

To provide an overall assessment, summary measures such as the incidence of (a) any adverse experiences; (b) any injection-site experiences; (c) any systemic adverse experiences; and (d) any vaccine-related adverse experiences will be summarized in both groups. Adverse experiences will be summarized as frequencies and percentages by vaccination group, by vaccination visit and across all vaccination visits. To address specific adverse experiences, the incidences of injection-site adverse experiences Days 1 to 5 and specific systemic adverse experiences within 14 days postvaccination occurring in at least 1% of the subjects will be tabulated. Risk differences between the vaccination groups will be estimated and their 95% two-sided confidence intervals calculated, by the method of Miettinen and Nurminen [33].

Statistical testing of no difference in safety parameters between the vaccine and placebo group will be restricted to injection site adverse experiences prompted for on the VRC (namely, injection site pain, redness and swelling), and for temperature elevations (maximum oral equivalent temperature  $\geq 37.5^{\circ}\text{C}$ ), across all vaccination visits. The testing will use the method of Miettinen and Nurminen [33] for a difference in proportions.

Tables of specific adverse experiences will be restricted to those events occurring in at least 1% of either vaccination group. Tables will also be generated for the subsets of subjects who were seropositive to at least one of the vaccine HPV types at Day 1, and who were seronegative to all vaccine HPV types at Day 1.

The incidence of greatest adverse experience intensity (mild, moderate, severe) reported by a subject will be tabulated for: all injection site adverse experiences (Day 1 to Day 5 following any vaccination visit); all systemic adverse experiences (Day 1 to Day 14 following any vaccination visit); any adverse experience (Day 1 to Day 14 following any vaccination visit). For those injection site events which are measured (redness and swelling), 0 to 1 inch would be categorized as mild, >1 inch to 2 inches will be categorized as moderate and >2 inches will be categorized as severe. Similar tables will be produced summarizing the greatest intensity per subject for each of the prompted adverse experiences individually.

The distribution of maximum temperatures recorded from Day 1 to Day 5 following each injection on VRCs will be summarized. The proportions of subjects who experience a maximum temperature of at least  $37.5^{\circ}\text{C}$  (oral equivalent) across all vaccination visits and by visit, will be provided.

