### **4.2.3.3 Safety Endpoints**

Since majority of the adverse events (AEs) occurs within a few days after the vaccination, the subjects will be followed for 14 days following each vaccination. The Vaccination Report

Card (VRC) will be utilized to collect subject's (1) oral temperature and local (i.e., injection-site) AEs (including erythema, swelling and pain/tenderness) for 5 days starting the day of each vaccination, (2) systemic AEs and serious adverse events (SAEs) for 15 days (14 days following each vaccination), and (3) vaccine-related SAEs and deaths throughout the study.

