#### **7.1.2.3 Vaccination Report Card (VRC)**

Each subject will receive a VRC at the study vaccination visit. On the VRC, the subject will be asked to record his oral temperature in the evening after each study vaccination and daily for 4 days after each study vaccination for the purpose of identifying febrile events. Also, beginning after each study vaccination and for a total of 15 days including the day of vaccination, the subject will be asked to record injection-site and systemic adverse experiences, concomitant medications, and concomitant vaccinations on the VRC. The information on VRC should be generated only by the subject and must be signed and dated by the subject to confirm the accuracy of the recorded information. The subject will be asked to bring the VRC to the study site at the next scheduled visit.

When the VRC is returned, the VRC should be reviewed for completeness by study site personnel. If clarification is needed, the study site personnel will discuss the VRC with the subject. Original information on the VRC should never be altered by study personnel, although comments can be written in the designated area for study site personnel on the front

of the VRC. Only the subject can make corrections to his information on the VRC. Any corrections to the VRC should be made by using an ink pen to add the omitted data and/or to draw a single line through the error and add the correct information. The subject should initial/date all VRC corrections.

All VRC information will be recorded in the Electronic Data Capture (EDC) system. The physician investigator/sub-investigator will determine causality of systemic and injection-site adverse experiences recorded on the VRC using the reporting guidelines given in the protocol and will classify each event as a serious adverse experience (SAE) or non-serious adverse experience (NSAE). If an oral temperature indicates a fever (defined as an oral temperature of  $\geq 37.5^{\circ}\text{C}$ ), the adverse experience of "fever" must be documented in the eCRFs. At the time of VRC review at the next scheduled visit, subjects will be questioned regarding any new medical conditions that occurred beyond Postdose Day 15. The physician investigator/sub-investigator will determine if the medical condition is to be reported as an SAE using the reporting guidelines provided in Section 7.2.2.1.

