### **8.2.3.3 Safety Endpoints**

Safety assessment will focus on the injection site adverse experiences/vaccine-related adverse experiences prompted for on the VRC occurring Day 1 through Day 5 following any vaccination, elevated temperature from Day 1 to 5 following any vaccination and systemic adverse experiences/vaccine-related adverse experiences occurring Day 1 through Day 15 following any vaccination. Serious adverse experiences occurring Day 1 through Day 15 following any vaccination, serious vaccine-related adverse experiences and new medical condition occurring any time during the study will be summarized.

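### The greatest-intensity tables for systemic and any adverse experiences cover Day 1 to Day 14, one day short of the 15-day diary and the Day 1 through Day 15 safety endpoint

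*Combined protocol and SAP*

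**What the plan says.** Section 8.2.5.3 specifies tables of the greatest intensity (mild, moderate, severe) reported by a subject, with three windows:

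- injection-site events: "all injection site adverse experiences (Day 1 to Day 5 following any vaccination visit"
- systemic events: "all systemic adverse experiences (Day 1 to Day 14 following any vaccination visit"
- any event: "any adverse experience (Day 1 to Day 14 following any vaccination visit"

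Other sections set a longer window for systemic events. Section 8.2.3.3 defines the safety endpoint as "systemic adverse experiences/vaccine-related adverse experiences occurring Day 1 through Day 15 following any vaccination". Section 7.1.2.3 has the subject complete the Vaccination Report Card "for a total of 15 days including the day of vaccination". Section 4.2.3.3 says the card collects "systemic AEs and serious adverse events (SAEs) for 15 days (14 days following each vaccination", which shows how the two ways of counting relate.

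The incidence tables of specific systemic events, also in Section 8.2.5.3, are limited to events within 14 days after vaccination. Section 8.2 says that no separate SAP is planned, so this text is the governing specification.

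**The concern.** The intensity sentence appears to have turned a period of 14 days after vaccination into an end point of Day 14. These differ by one day when Day 1 is the vaccination day. No reason is given for a shorter intensity window.

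What is at stake is the internal consistency of the tolerability reporting. Tolerability is the second primary objective in Section 3.1, and intensity is part of its planned summary. A programmer who follows the sentence produces an intensity table that does not match the endpoint as defined. A programmer who silently uses Day 15 departs from the written plan, and Section 8.2 requires changes to planned analyses to be listed and explained in the study report.

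**Working it through.** This is a day count; no sample-size or alpha formula applies. The count of days in a window is last day − first day + 1.

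**1. The plan's own figure.** Section 4.2.3.3 equates 15 days with the vaccination day plus the 14 days that follow: 1 + 14 = 15. Section 7.1.2.3 gives the same total. The figure is reproduced.

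**2. Windows compared.**

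| Source | Window | Days |
|---|---|---|
| Diary (4.2.3.3, 7.1.2.3) | vaccination day + 14 days | 1 + 14 = 15 |
| Systemic endpoint (8.2.3.3) | Day 1 through Day 15 | 15 − 1 + 1 = 15 |
| Intensity tables, systemic and any event (8.2.5.3) | Day 1 to Day 14 | 14 − 1 + 1 = 14 |
| Intensity table, injection site (8.2.5.3) | Day 1 to Day 5 | 5 − 1 + 1 = 5 |

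**3. Gap.** 15 − 14 = 1 day per dose. Over three doses, 3 × 15 − 3 × 14 = 45 − 42 = 3 days. As a share of diary days this is 1/15 = 6.7%.

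**4. Can another day numbering close the gap?**

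- *Vaccination day = Day 1.* The injection-site window of Day 1 to Day 5 then equals the collection period in Section 4.2.3.3, "for 5 days starting the day of each vaccination". Under the same numbering the systemic window stops a day early and Day 15 is left out.
- *Vaccination day = Day 0.* The diary then runs from Day 0 to Day 14. Day 1 to Day 14 is again 14 days, and the vaccination day itself is left out. The injection-site window in the same sentence would also no longer match its collection period.

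Neither numbering makes the window cover all 15 days. The first is the one that fits the rest of the sentence.

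**5. Who is affected.** The table counts subjects by their greatest intensity over all vaccinations. On the first numbering:

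- A subject whose only systemic event starts on Day 15 does not appear with an intensity.
- A subject with a moderate systemic event in the first few days and a severe one starting on Day 15 is tabulated as moderate.
- A subject who has an event at least as intense on any other covered day, after any dose, is tabulated correctly.

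**6. Reconciliation.** The mismatch with the endpoint in Section 8.2.3.3 is direct. The mismatch with the incidence tables of specific systemic events needs one step: by the conversion in Section 4.2.3.3, 14 days after vaccination ends on Day 15. The overall summary measures in Section 8.2.5.3 carry no stated window, so nothing can be concluded about those.

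**The case against.** The strongest reply is that the per-dose meaning of Day 1 is inferred. The documents define Day 1 only as the date of dose 1 (footnotes to Tables 4 and 5, where that date takes the value 0). Table 2 in Section 7.2.3 numbers differently: it assesses injection-site redness and swelling from the day of vaccination through Day 4 post-vaccination. On that scale the last diary day is Day 14, and the intensity sentence could be loose wording for the full window. This stands as a reason not to be certain which day would be lost. It does not rescue the text, because the window starts at Day 1 and is one day short under either numbering (step 4).

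The second reply concerns size, and it stands. A reader might infer that about 7% of systemic events, or of severe ones, vanish from the safety report. The documents do not support that. The 6.7% is a share of calendar days, whereas the table counts subjects by greatest intensity. Treating it as a share of events would need uniform onset, and Section 4.2.3.3 says most events occur within a few days. Day 15 systemic events also remain within the endpoint in Section 8.2.3.3.

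A reader might also infer that serious events are lost. Table 2 treats intensity and seriousness as separate attributes, and Section 8.2.3.3 summarizes "Serious adverse experiences occurring Day 1 through Day 15 following any vaccination" and vaccine-related serious events at any time.

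Third, no inference depends on these tables. Safety testing in Section 8.2.5.3 is restricted to prompted injection-site events and temperature elevation, whose Day 1 to Day 5 windows agree across sections. The tolerability objective has no statistical criterion, and Section 8.1.2 names vaccine-related serious events as the primary safety interest. This also stands.

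**Conclusion.** The inconsistency is real and the intensity sentence is wrong as written. Its window is 14 days where the diary and the endpoint have 15, in two of the three intensity tables; the injection-site table is correct. The consequence is limited to subjects whose only or worst event starts on the omitted day, in a descriptive summary. The documents give no onset distribution by day, so the number of such subjects cannot be computed; early onset suggests it is low. That the omitted day is Day 15 rests on taking Day 1 as the vaccination day, which the injection-site window in the same sentence supports. Efficacy, power, alpha and the planned safety tests are unaffected. This is a minor correction.

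**What to change.** In the intensity paragraph of Section 8.2.5.3, change Day 14 to Day 15 for systemic adverse experiences and for any adverse experience. State once, for all safety windows, that Day 1 is the day of each vaccination. Relabel the end of the redness and swelling period in Table 2 (Section 7.2.3) as Day 5 under that numbering; the five days it covers stay the same.

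The cost is a few words of text. The Day 15 data are already collected on the Vaccination Report Card, so no procedure, data collection or statistical method changes.

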### **8.2.5.4 Subgroup Analyses and Effect of Baseline Factors**

The impact of baseline characteristics on efficacy outcomes will be explored by presenting vaccine efficacy estimates within subsets defined by the characteristics listed in Section 8.2.5.1.

Data permitting, all the planned analysis will be provided both for HM and MSM subgroups.

### 8.2.6 Multiplicity

This study tests one primary endpoint which is performed at up to 2 analysis times (1 interim analysis and a final analysis).

The overall probability of making a false claim of superiority, across the two analysis times, is controlled at level 0.025. The nominal alpha levels for positive vaccine efficacy findings were 0.006 at interim analysis and 0.02273 at final analysis. One formal interim analysis for the primary endpoint will be conducted during the study. The gamma spending function, used for alpha on endpoints as outlined by Hwang, Shih, and DeCani [34] was used in calculation. The information time for the interim analyses will be based on the proportion of events observed during the study.

### 8.2.7 Sample Size and Power Calculations

This study will enroll approximately 1100 subjects. For Asian males in Protocol V501-020, the observed incidence rate for HPV6/11/16/18-related Persistent Infection among placebo recipients was 2.3 per 100 person-years with the vaccine efficacy of 100%. If the true incidence rate on HPV6/11/16/18-related Persistent Infection is 2.3 per 100 person-years in Japanese males, with the assumption of vaccine efficacy of 85%, about 59% of enrolled subjects with evaluable data and one interim analysis at time of 11 persistent infection cases observed, the study will have at least 90% power to achieve success for the primary hypothesis. The total persistent infection cases needed to keep the power is 18. With the assumption of vaccine efficacy of 90%, the study will have more than 98% power to achieve success for the primary hypothesis. The power for a given number of observed primary endpoints was computed using the method of Chan and Bohidar [35]. The statistical criterion for success requires that the lower bound of the two-sided 95% confidence interval for vaccine efficacy be greater than 0. The rate of drop-out is estimated as 0.41 based on V501 PN020 study. The details are as follows: no general protocol violation 95%; exclusion rate due to Day1 seropositive or PCR positive between Day 1 and Month 7 to HPV 6, 11, 16, and 18 is not greater than 15%; 90% of randomized subjects completed vaccination phase and 80% of Month 7 subjects completed 30-months' follow-up period.

### 8.2.8 Interim Analysis

One interim analysis will be performed in this study. Results will be reviewed by a DMC. The endpoint, timing, and purpose of the interim analysis are summarized in [Table 7](#) below.

Table 7 Summary of Interim Analysis Strategy

Endpoint for interim Analysis	Timing of Interim Analysis	Purpose of Interim Analysis
HPV6/11/16/18 related persistent infection	11 persistent infection cases are documented across the 2 arms	Getting significant VE results earlier

The main purpose of the interim analysis is to make a superiority claim earlier. The primary endpoint at interim analysis is to be tested with overall one-sided alpha = 0.006. The spending function preserves much of the alpha for the final analysis (alpha=0.02273). The exact method was used to calculate the actual alpha spending in interim analysis [35] and HSD method was used to decide the alpha for the final analysis [34]. If one or less persistent

infection case is observed in vaccine group among total 11 persistent infection cases, significant results can be reached. If the true vaccine efficacy is 85% we have 57% probability to make a superiority claim. With vaccine efficacy of 90%, the probability will increase to 73.6%

The decision rules are driven by the one-sided p-values and vaccine efficacy, [Table 8](#) summaries the alpha spending and corresponding powers at interim analysis and final analysis. Interim analysis will be conducted by an unblinded statistician.

Table 8 Alpha Spending and Corresponding Powers at Interim Analysis and Final Analysis

Vaccine Efficacy	Interim analysis		Final Analysis		Overall Significant Probability
	Boundary p-values	Significant Probability	Boundary p-values	Significant Probability	
85%	0.006	57.0%	0.0227	83.1%	92.7%
90%	0.006	73.6%	0.0227	93.0%	98.1%

At Interim Analysis, the frequency of adverse experiences among vaccinated patients will also be evaluated in each vaccination group.

An independent DMC will carefully monitor the formal safety and efficacy interim results of this trial. In terms of efficacy, the DMC will use the guidelines proposed below for recommendation of either continuation or early termination of the study at the interim analysis. Additionally, the DMC will review safety data of the ongoing study at close, regular intervals as specified in the DMC charter. Such safety data will be summarized by blinded vaccination groups. A detailed description of the structure, function, and guidelines for decision-making by the DMC are also outlined in the DMC charter.

### 8.2.9 Compliance

Compliance is defined in this study as receipt of all scheduled study vaccinations. The numbers of subjects who receive each vaccination will be tabulated by vaccination group. The numbers of subjects who complete each follow-up visit will be tabulated by vaccination group. The numbers of subjects with biopsies or excision procedures performed outside of the study and the numbers of these subjects for whom the tissue samples were not available, will be tabulated by vaccination group. Differences in these numbers will be assessed observationally and the potential impact on the efficacy analyses noted. Exposure to vaccine will be summarized by tabulating the number of subjects receiving each of the three study vaccinations.

### 8.2.10 Missing Data

There will be no imputation of results where data are missing. Biopsy samples with missing PCR results cannot be counted as a case for the primary analysis.

## **9.0 LABELING, PACKAGING, STORAGE AND RETURN OF CLINICAL SUPPLIES**

### **9.1 Investigational Product**

The investigator shall take responsibility for and shall take all steps to maintain appropriate records and ensure appropriate supply, storage, handling, distribution and usage of investigational product in accordance with the protocol and any applicable laws and regulations.

Clinical Supplies will be provided by the Sponsor as summarized in [Table 9](#).

Table 9 Product Descriptions

Product Name & Potency	Dosage Form
V501 (Quadrivalent HPV Vaccine) 20/40/40/20 µg/0.5 mL HPV types 6/11/16/18 or matching Placebo	Sterile suspension for IM injection

### **9.2 Packaging and Labeling Information**

Clinical supplies will be affixed with a clinical label in accordance with regulatory requirements.

Subjects will receive one (1) blinded vial of V501 or matching placebo at Day 1 (Visit 1), Month 2 (Visit 2) and Month 6 (Visit 3). No kitting is required.

### **9.3 Clinical Supplies Disclosure**

Supplies will be provided with random code/disclosure envelopes or lists containing drug disclosure information. The Sponsor will provide one sealed envelope to the central emergency unblinding center for each randomization number.

Drug identification information is to be unmasked ONLY if necessary for the welfare of the subject. Every effort should be made not to unblind the subject unless necessary.

In the event that unblinding has occurred, the circumstances around the unblinding (e.g., date and reason) must be documented promptly, and the Sponsor Clinical Monitor notified as soon as possible. Only the principal investigator or delegate and the respective subject's code should be unblinded. Trial site personnel and Sponsor personnel directly associated with the conduct of the trial should not be unblinded.

### **9.4 Storage and Handling Requirements**

Clinical supplies must be stored in a secure, limited-access location under the storage conditions specified on the label.

Receipt and dispensing of trial medication must be recorded by an authorized person at the trial site.

Clinical supplies may not be used for any purpose other than that stated in the protocol.

